4.3 Complementary Assessment of External Samples/Data

External blood samples/data from different sources will be analyzed as complementary analysis to further assess the immunogenicity profile of study vaccine.

The external blood samples/data from different sources will be analyzed separately by sample repository and combined as one per the primary series vaccine.

The sample selected from external sources are from adults, ≥ 18 years of age. As the samples are de-identified, other demographic and baseline characteristics are not available. The time point of blood samples are based on time interval of pre-vaccination and post-vaccination matched with the VAT00002 study time intervals as closely as possible. The external data is considered as belong to naïve participants before COVID-19 vaccination, however, no exact match to the study definition could be applied, for example, the participants are presumed to be naïve to SARS-CoV-2 base on antibody levels.

The Monogram assay will be used to evaluate immune responses in the blood samples.

GMTs in each and combined sample repository, and GMT ratios between external data group and booster arm will be descriptively summarized along with their 95% CIs using the normal approximation of log-transformed titers. GMTs will be presented in original scale that are re-converted from log-transformed titers. The 95% CI of GMT ratios between groups will be based on the Welch's t-interval for primary series vaccination group and booster arm, the 95% CI of GMT ratios between primary series vaccination groups will be based on the Student t-distribution.

GMTR or GMCR will be summarized with 95% CI (Normal approximation).

Estimated seroresponse will be calculated by post dose versus pre dose with antibody titer. Additional parameters may be displayed as appropriate.

5 Changes in the Conduct of the Trial or Planned Analyses

- A pooled primary series cohort as Supplemental Cohorts 2 Comparator Group**

A Pooled Primary Series Cohort as Supplemental Cohorts 2 Comparator Group was added in Protocol Amendment 4, version 8. The purpose is to maintain sufficient power for Cohort 2 hypothesis testing in primary analysis in case of a substantial shortfall in numbers of Comparator Group evaluable participants as the number of authorized and/or approved COVID-19 vaccines increases and RDT at baseline sensitivity to identify the Naïve participants is low. The pooling of evaluable participants from other trials of the same vaccine program is defined in SAP and the exploratory sensitivity analysis is added.

- Complementary assessment of external samples/data**

To further study immunogenicity profile of study vaccine, external samples/data will be analyzed along with study data. The assessment of external samples/data is considered as complementary analysis and corresponding part is added in SAP Section 4.3.

- Study design updated to remove Variant Prime Cohort 3**

The operational feasibility of recruiting SARS-CoV-2 naïve, unvaccinated participants has become significantly more challenging, data are not required for regulatory purposes.

- Enlarge the variant testing scope of Cohort 1 and Cohort 2 (Protein Primed Group)**

A randomized subset of 70 participants in Cohort 1 was originally planned to be tested for additional SARS-CoV-2 variants of concern including Delta. However, to address CBER requests, the Sponsor decided to expand the scope of testing and to perform the immunogenicity assessment for Delta in the whole Cohort 1 and Cohort 2 (Protein Primed Group) instead of only in a subset of participants. Thus, the VTAS will not be applicable to Cohort 1 variant testing results. The PPAS and FAS will be utilized for analyzing the variant testing results.

- Modify variant testing subset analysis set definition**

The Variant Testing Subset Analysis Set (VTAS) will have the blood sample time window adherence considered in order to know the per-protocol participants immunogenicity response. The Variant Testing Subset without consider the exclusion criteria will be utilized to see the immunogenicity results furthermore.

- Add study duration and safety follow-up duration calculation method for ongoing participants in interim analysis**

The database lock or data extraction date will be utilized for calculation on study duration and safety follow-up duration in ongoing participants under interim analysis scope.

- Modify the analysis set utilized for Comparator Group on variant testing results**

The Naïve at D01+D22 Comparator Group participants will be used for Variant Testing results analyses. Consider the serostatus would be a factor to impact the immunogenicity response.

- **Add imputation rule for partial prior COVID-19 vaccination date**

In order to calculate the duration of prior COVID-19 vaccination to booster injection, the partial COVID-19 vaccination date (day is missing) will be imputed using the “01” day.

6 Supporting Documentation

6.1 Appendix 1 List of Abbreviations

AE	Adverse Events
AESI	Adverse events of special interest
AR	Adverse reactions
CRF	Case report form
DMC	Data Monitoring Committee
FAS	Full analysis set
FR	Fold rise
GCI	Global Clinical Immunology
GM	Geometric mean
GMT	Geometric mean titer
GMC	Geometric mean concentration
LLOQ	Lower level of quantitation
MAAE	Medically attended adverse event
MedDRA	Medical Dictionary for Regulatory Activities
NA	Not applicable
PPAS	Per-protocol analysis set
RCDC	Reverse cumulative distribution curve
SAE	Serious adverse events
SafAS	Safety analysis set
SAP	Statistical analysis plan
SOC	(Primary) System organ class
PT	Preferred term
TLF	Tables, listings and figures
ULOQ	Upper level of quantitation

7 References

1. Newcombe RG. Two-sided confidence intervals for the single proportion: comparison of seven methods. *Stat Med*. 1998;17(8):857-72.
2. Newcombe RG. Interval estimation for the difference between independent proportions: comparison of eleven methods. *Stat Med*. 1998;17(8):873-90.

8 Appendix A

Table 8.1: Table of Assay Information*

Protocol Section	Protocol Assay Name	Response Type	Testing Variants		Testing Timepoints		LLOQ/ULOQ	Short Name	Full Description	Used in Statistical Analysis
			Cohort 1, Cohort 2	Cohorts Comparator Group	Cohort 1, Cohort 2	Cohorts Comparator Group				
Immunogenicity Assays										
8.2.1.1	SARS-CoV-2 Pseudovirus Neutralization Assay	Continuous on Neutralizing antibodies (serum dilution conferring 50% inhibition (ID50))	D614G, B.1.351	D614G, B.1.351	All visits	All visits	LLOQ is 40 and ULOQ is 787339	Monogram neutralization antibodies	SARS-CoV-2 Pseudovirus Neutralization Assay at Monogram for variant strains	Primary immunogenicity, Secondary immunogenicity
8.2.2.3	SARS-CoV-2 Spike Protein Antibody Serum IgG ELISA	Continuous on Binding antibodies	D614	D614	All visits	All visits	LLOQ is 18.9	binding antibodies by ELISA	SARS-CoV-2 Spike Protein Antibody Serum IgG ELISA at Nexelis for matched vaccine strain (D614 parental)	Secondary immunogenicity

Protocol Section	Protocol Assay Name	Response Type	Testing Variants		Testing Timepoints		LLOQ/ULOQ	Short Name	Full Description	Used in Statistical Analysis
			Cohort 1, Cohort 2	Cohorts Comparator Group	Cohort 1, Cohort 2	Cohorts Comparator Group				
8.2.3.2	Cellular Immune Assays	Continuous on B cell memory responses (IgG, IgA) and	D614G	D614G	D01, D134, and D387	D01, D91, and D366	NA	B cell response	Cellular Immune Assays for B cell memory responses (IgG, IgA) at SP (REI)	Exploratory immunogenicity (Cellular immune response)
8.2.3.2	Cellular Immune Assays	Continuous on T-cells CD4+ / CD8+	D614G	D614G	D01, D29, D91, and D366	D01, D22, D36, D134 and D387	NA	T cell response	Cellular Immune Assays for CD4+ / CD8+ T-cells at FH	Exploratory immunogenicity (Cellular immune response)
8.2.3.3	Mucosal Antibody assays	Continuous on total antibodies to SARS- Continuous on CoV-2 in human oral fluid specimens	D614	D614	D01, D15 and D91	D01, D22, D36 and D134	NA	Saliva antibodies	Mucosal Antibody assays for total antibodies to SARS-CoV-2 in human oral fluid specimens at SP (GCI lab)	Exploratory immunogenicity (Mucosal antibody response)

Protocol Section	Protocol Assay Name	Response Type	Testing Variants		Testing Timepoints		LLOQ/ULOQ	Short Name	Full Description	Used in Statistical Analysis
			Cohort 1, Cohort 2	Cohorts Comparator Group	Cohort 1, Cohort 2	Cohorts Comparator Group				
8.2.3.5	SARS-CoV-2 Pseudovirus Neutralizing Assay (Nexelis)	Continuous on Neutralizing SARS-CoV-2 pseudovirus antibodies	D614G, B.1.1.7, P.1, B.1.617, etc.	D614G, B.1.1.7, P.1, B.1.617, etc.	D01, D15, D29, D181 and D366	D01, D36, D202 and D387	To be determined	Nexelis neutralization antibodies	SARS-CoV-2 Pseudovirus Neutralization Assay at Nexelis for variant strains	Secondary immunogenicity, Exploratory immunogenicity (variant strains analysis)
Diagnostic Assays										
8.1.5.3	ELECSYS Anti-SARS-CoV2 Anti-S ECLIA	Categorical on SARS-CoV-2 infection status (positive/negative/NR)	NA	NA	D01	D01	NA	NA	NA	Prior SARs-CoV-2 Naïve/Non-Naïve status
8.1.6	NAAT Assessment Prior to Vaccination	Categorical OR continuous on SARS-CoV-2 infection status (positive/negative/NR)	NA	D01	D01, D22 and all CLI01	D01, D22 and all CLI01	NA	NA	NA	Prior SARs-CoV-2 Naïve/Non-Naïve status, COVID related endpoints

* Assay information are based on the current best knowledge and potential to be updated when more information become available.

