At the CLI01 visit, participants will be provided with a pulse oximeter and asked to record pulse oximetry readings twice a day from onset of illness until the results of the respiratory swab collected for NAAT testing at CLI01 are available. Continuation of pulse oximetry readings by the participant after availability of test results will be based on Investigator judgment.

‡ Follow-up telephone call approximately 30 days after onset of illness. If symptoms are ongoing 30 days after illness onset, a second telephone call 60 days after onset of illness will be scheduled.

Table 1.2: Planned sample sizes for Supplemental Cohorts 1 and 2

		Cohort 1	Cohort 2 Main Arms			Comparator *
		Booster	Booster	Booster	Booster	Primary Series
		CoV2 preS dTM-AS03 (D614)	CoV2 preS dTM-AS03 (B.1.351)	CoV2 preS dTM-AS03 (D614 + B.1.351)	CoV2 preS dTM-AS03 (D614)	CoV2 preS dTM-AS03 (D614)
Total Overall		565	970	865	345	515
SARS-CoV-2-naïve, Unvaccinated Adults (18-55 years)						515
Pfizer/BioNTech	Adults (18-55 years)	215	515	515	--	
	Older adults (≥ 56 years)	50	50	50	--	--
CoV preS dTM-AS03 (Original Phase II Cohort)	Adults (18-55 years)	--	30	--	270	--
	Older adults (≥ 56 years)	--	75	--	75	--
Moderna	Adults (18-55 years)	75	75	75	--	--
	Older adults (≥ 56 years)	25	25	25	--	--
Oxford University/ AstraZeneca	Adults (18-55 years)	75	75	75	--	--
	Older adults (≥ 56 years)	25	25	25	--	--
J&J/Janssen	Adults (18-55 years)	75	75	75	--	--
	Older adults (≥ 56 years)	25	25	25	--	--

Table 1.3: Planned sample sizes for Supplemental Cohort 2 Exploratory B.1.351 Arms

		CoV2 preS dTM-AS03 (B.1.351) Treatment Groups			
		2.5 µg with full-dose AS03	5 µg with half-dose AS03	5 µg with no adjuvant	2.5 µg with half-dose AS03
Total Overall		100	100	100	100
Age Groups	Adults (18-55 years)	75	75	75	75
	Older adults (≥ 56 years)	25	25	25	25

Supplemental Cohort 1 and Cohort 2 Booster Arms Only: all participants will receive a single booster dose (VAC) at D01. Blood samples will be collected from all participants prior to the booster injection, 14 days, 1 month, 3 months, 6 months, and 12 months after the injection.

Supplemental Cohorts Comparator Group: all participants will receive 2 vaccine injections given 3 weeks apart: the first injection will be at D01 (VAC1) and the second injection will be at D22 (VAC2). Blood samples will be collected from all participants prior to each injection, 14 days, 4 months, 6 months, 9 months, and 12 months after last injection.

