
Supplemental Cohorts 1 and 2:
 
 To describe the neutralizing antibody response to emergent SARS-CoV-2 variant strains To further describe humoral immune responses based on relevant emerging assays, if applicable 
Supplemental Cohort 2:
 
 To assess the cellular immune response at D01, D15, D29, D91, and D366 in a subset of participants. To assess the mucosal antibody response at D01, D15, and D91 in a subset of participants. To describe the neutralizing antibody response to emergent SARS-CoV-2 variant strains To further describe humoral immune responses based on relevant emerging assays, if applicable 
Supplemental Cohorts 1 and 2:
 
 To describe the neutralizing antibody response, by presence or absence of baseline high-risk medical conditions 	
Endpoints for exploratory immunogenicity objective #1 and #5:
 
Neutralizing antibody responses to emergent variant strains will be measured:
 
 Individual serum neutralizing titer at each pre-defined time point Individual serum neutralization titer fold-rise post-vaccination relative to D01 at each pre-defined time point \geq 2-fold-rise and \geq 4-fold-rise in serum neutralization titer [post/pre] at each predefined post-vaccination timepoint Responders, defined as participants who had baseline values below LLOQ with quantifiable neutralization titer above assay LLOQ at each pre-defined post-vaccination timepoint and participants with baseline values above LLOQ with a 4-fold increase in neutralizing antibody titers at each pre-defined post-vaccination timepoint 
Endpoint for exploratory immunogenicity objective #2 and #6:
 
Biomarker measurement at baseline and/or post-vaccination visits
 
Endpoint for exploratory immunogenicity objective #3:
 
 Other CMI assessments may be performed by Intracellular Cytokine Staining or/and enzyme-linked immunospot (ELISpot) assays. 
Endpoints for mucosal antibody responses (objective #4) will be specified in a supplemental analysis plan
 
Endpoints for exploratory immunogenicity objective #7:
 
Neutralizing antibody responses to D614G and B.1.351 strains will be measured:
 
 Individual serum neutralizing titer at each predefined time point Individual serum neutralization titer fold-rise post-vaccination relative to D01 at each pre-defined time point \geq 2-fold-rise and \geq 4-fold-rise in serum neutralization titer [post/pre] at each predefined post-vaccination timepoint

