
Cellular Immunity and Mucosal analysis set (CMIAS)
	
Subset of the FAS and randomly assigned to the Cellular Immunity and mucosal subset (Original Phase II Cohort, Supplemental Cohort 2 primed with Pfizer/BioNTech vaccine in the non-exploratory groups, Supplemental Cohort 2 CoV2 preS dTM-AS03 (D614) primary series from the Original Phase II Cohort). Participants presenting with at least one of the following criteria will be excluded from the CMIAS:
 
 • Participant did not meet all protocol-specified inclusion criteria or met at least one of the protocol-specified exclusion criteria • Participants did not receive both injections in the primary vaccination groups or one injection in the booster vaccination groups • Participant received a vaccine other than the one that he / she was randomized to receive • Preparation and / or administration of vaccine was not done as per-protocol • Participant did not receive vaccine in the proper time window • Participants received the second injection (in the primary vaccination groups) despite meeting any of the definitive contraindication criteria. • Participant receives an authorized/approved COVID-19 vaccine prior to D36 for primary vaccination groups or D15 for booster vaccination groups 
The definition may be complemented with additional criteria for exclusion after the review of protocol deviations reported on site.

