3.3.1 Analysis sets Used in Analyses

The analysis set used in analyses is listed in [Table 3.2](#).

Table 3.2: Analysis set used in analyses

Cohort	Type of Analyses		Intervention group(s)	Comparator group
Supplemental Cohort 1, Supplemental Cohort 2	Primary immunogenicity	Main	PPAS	PPAS Naïve at D01+D22
		Sensitivity	FAS	FAS Naïve at D01 FAS Naïve at D01+D22
	Secondary immunogenicity	Main	PPAS	PPAS Naïve at D01+D22
		Sensitivity	FAS	FAS Naïve at D01 FAS Naïve at D01+D22
	Exploratory immunogenicity regarding objective #11		PPAS	PPAS Naïve at D01+D22
	Exploratory immunogenicity in CMI subset for Cohort 2		CMIAS	CMIAS
	Exploratory immunogenicity in Variant Testing subset		VTAS Variant Testing Subset	VTAS Naïve at D01+D22 Variant Testing Subset Naïve at D01+D22
Supplemental Cohorts	Primary, Secondary safety		SafAS	SafAS

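### Table 8.1 swaps the booster and Comparator B-cell testing days and lists no booster cellular assay at D15, contrary to exploratory objective 3

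*SAP*

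**What the plan says.** - **Objective.** In Section 2, Table 2.1, exploratory objective 3 for Supplemental Cohort 2 reads: "To assess the cellular immune response at D01, D15, D29, D91, and D366 in a subset of participants".
- **B-cell row, Section 8 (Appendix A), Table 8.1.** The timepoint columns are headed first for Cohorts 1 and 2, then for the Comparator Group. The first holds "D01, D134, and D387", the second "D01, D91, and D366".
- **T-cell row, same table.** The booster column holds "D01, D29, D91, and D366", the Comparator column "D01, D22, D36, D134 and D387".
- **Booster visits.** Section 1 has booster-arm blood drawn "prior to the booster injection, 14 days, 1 month, 3 months, 6 months, and 12 months after the injection", with about 366 days of participation. The objectives in Table 2.1 name the visits as D01, D15, D29, D91, D181 and D366.
- **Comparator visits.** Section 1 has Comparator blood drawn before each injection (D01 and D22), then 14 days and 4, 6, 9 and 12 months after the last one.
- **Analysis.** Section 3.4.6 summarises B- and T-cell data as GMTs with 95% CIs in the CMIAS, and refers to Appendix A for assay details.
- **Comparator in the cellular analysis.** Table 3.2 has a row "Exploratory immunogenicity in CMI subset for Cohort 2" that enters CMIAS for the Comparator as well as for the intervention groups. The CMIAS definition in Section 3.3 lists the Original Phase II Cohort, "Supplemental Cohort 2 primed with Pfizer/BioNTech vaccine in the non-exploratory groups", and the Cohort 2 participants primed with the study vaccine. It does not list the Supplemental Cohorts Comparator Group.

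**The concern.** Table 8.1 is the only place in the SAP that gives cellular testing days assay by assay. Someone who programs the tables or writes the testing request from it would look for booster B-cell results on two days when no booster participant has a visit, and would find baseline values only. The memory B-cell response after the booster would then go unreported. The early T-cell response, 14 days after the booster, would be absent although the objective names that day. A programmer also cannot tell whether the Comparator column of the cellular output is meant to be filled.

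**Working it through.** No power or alpha calculation applies. The check compares three lists of days: the objective's, the booster visits and Table 8.1.

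**1. To which group do D134 and D387 belong?** The Comparator's second injection is at D22.
- D134 − D22 = 112 days; 112 / 30.44 = 3.7 months, which fits the 4-month draw.
- D387 − D22 = 365 days; 365 / 30.44 = 12.0 months, which fits the 12-month draw.
- Counted from a booster at D01: 133 / 30.44 = 4.4 months and 386 / 30.44 = 12.7 months. Neither is a booster visit, and D387 is 387 − 366 = 21 days past the last one.

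Conversely, the days printed for the Comparator (D91 and D366) are booster visits.

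**2. Is the whole table reversed, or one row?**

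| Row | Cohorts 1 and 2 | Comparator |
|---|---|---|
| B cell | D01, D134, D387 | D01, D91, D366 |
| T cell | D01, D29, D91, D366 | D01, D22, D36, D134, D387 |
| Saliva | D01, D15, D91 | D01, D22, D36, D134 |
| Nexelis neutralization | D01, D15, D29, D181, D366 | D01, D36, D202, D387 |

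Only the B-cell row carries Comparator days under the boosters. The other three rows keep their order, so a misread table layout is unlikely.

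**3. Coverage of objective 3 (D01, D15, D29, D91, D366) in the booster arms**

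| Testing list | Objective days met | Not met |
|---|---|---|
| B cell as printed | 1 of 5 (D01) | D15, D29, D91, D366 |
| B cell after exchange | 3 of 5 (D01, D91, D366) | D15, D29 |
| T cell as printed | 4 of 5 (D01, D29, D91, D366) | D15 |
| Both assays, as printed or after exchange | 4 of 5 | D15 |

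The exchange repairs the B-cell row but leaves D15 without any cellular assay. The booster saliva days match those of exploratory objective 4 (D01, D15, D91), so the table appears intended to follow the objectives.

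**4. Does the Comparator belong to the cellular and mucosal subset?**
- Pointing to yes: Section 1 says that whole blood, PBMCs and saliva come from a subset within every cohort; Table 3.2 assigns the Comparator a CMIAS; Table 8.1 gives it cellular and saliva days.
- Pointing to no: the CMIAS definition omits it, while the parallel VTAS definition names it; Table 1.4 places its 26 participants in the column reserved for variant testing; the Figure 1.2 legend (Comparator) has no mononuclear-cell or saliva symbol, while the Figure 1.1 legend (boosters) has both.

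**The case against.** The strongest reply is that Table 8.1 is an assay-information appendix and not the operating schedule. Section 4 refers to the protocol for procedures, the cellular rows cite protocol section 8.2.3.2, and a footnote marks the table as open to update. A booster participant cannot attend D387, so the slip shows itself. Objective 3 also lists its days for the cellular response as a whole, not for each assay, and its endpoint is worded permissively.

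Much of this stands as a limit on the consequence. It does not remove the error. A provision for later updating does not cover a reversed row or a day that the SAP's own objective names and the table omits. Reading the objective collectively excuses the B-cell row for lacking D29, which the T-cell row covers. It does not excuse D15, which neither row covers.

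Two stronger readings are tempting, and the document does not support them:

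- **That the objective cannot be derived from the samples the trial takes.** Table 8.1 lists testing days, not collection days. Booster blood is drawn at D15, D91 and D366. The mononuclear-cell sampling days are in Figure 1.1, which could not be consulted here. Nothing available shows a missing sample, and T-cell response remains derivable at four of the five days.
- **That the Comparator's CMIAS column is empty and its entries should be deleted.** The passages conflict in both directions. The CMIAS definition also includes the Original Phase II Cohort and a both-injections criterion for primary-series groups, so a primary-series population might be meant for that column. Deletion would settle the conflict one way without grounds.

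**Conclusion.** The error is real and limited. Table 8.1 reverses the booster and Comparator B-cell testing days and gives the booster arms no cellular assay at D15, against exploratory objective 3. If the table is followed as printed, neither of the two post-baseline B-cell days can be met in the booster arms, and the D15 cellular response is not tested. T-cell response at D01, D29, D91 and D366 is unaffected.

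The objective is exploratory, is addressed in a planned subset of 82 younger adults, and is summarised descriptively, so no confirmatory analysis is touched. Whether the Comparator belongs to the cellular and mucosal subset is a separate, unresolved contradiction. The conclusion rests on the column order in the Table 8.1 header, which the T-cell, saliva and Nexelis rows confirm. Whether any data would actually be lost depends on the testing instructions in use, which the SAP does not show.

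**What to change.** 1. In Table 8.1, exchange the two B-cell timepoint entries: boosters D01, D91 and D366; Comparator D01, D134 and D387, if the Comparator is tested at all.
2. Check the actual cell-sampling schedule for D15. If cells are drawn then and testing is intended, add D15 to the relevant cellular row. Otherwise remove D15 from objective 3.
3. State once whether the Comparator belongs to the cellular and mucosal subset. Then bring Section 1 (including Table 1.4 and Figure 1.2), the CMIAS definition, Table 3.2 and Table 8.1 into line. If the Table 3.2 entry is meant to be the Original Phase II primary-series participants, say so.

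The cost is a correction to one appendix table and a few lines elsewhere, with no change to any confirmatory analysis. New testing would arise only if D15 is kept and has not been tested. New sampling would arise only if cells have not been drawn on that day.
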